3. PATIENT SELECTION

3.1 Eligibility Criteria

- 3.1.1 Patients must have documented *EWSR1/ATF1* or *EWSR1/CREB1* translocation or histologically confirmed clear cell sarcoma, documented grade 2 or 3 conventional chondrosarcoma, or documented dedifferentiated chondrosarcoma. The disease must not be curable by surgery.
- 3.1.2 Patients must have measurable disease, defined as at least one lesion that can be accurately measured in at least one dimension (longest diameter to be recorded for non-nodal lesions and short axis for nodal lesions) as ≥ 20 mm (≥ 2 cm) by chest x-ray or as ≥ 10 mm (≥ 1 cm) with CT scan, MRI, or calipers by clinical exam. See Section [11](#) (Measurement of Effect) for the evaluation of measurable disease.
- 3.1.3 Patients with newly diagnosed, unresectable, metastatic and measurable clear cell sarcoma, *EWSR1/ATF1* or *EWSR1/CREB1* translocation, grade 2 or 3 conventional chondrosarcoma, or dedifferentiated chondrosarcoma will also be eligible if they show clinical evidence of disease progression (including history and increasing physical symptoms). On-study documentation will include a physician’s rationale that supports

evidence of clinical disease progression (i.e., increasing tumor pain).

3.1.4 Age ≥ 2 years at the NCI Clinical Center (≥ 12 years at other participating sites)

3.1.5 ECOG performance status ≤ 2 (Karnofsky or Lansky $\geq 70\%$, see [Appendix A](#)).

3.1.6 Life expectancy of greater than 3 months.

3.1.7 Patients must have adequate organ and marrow function as defined below:

- absolute neutrophil count $\geq 1,000/\text{mcL}$
- platelets $\geq 100,000/\text{mcL}$
- hemoglobin $\geq 8 \text{ g/dL}$
- total bilirubin \leq institutional upper limit of normal (ULN)
(however, patients with known Gilbert disease who have serum bilirubin level $\leq 3 \times \text{ULN}$ may be enrolled)
- AST(SGOT)/ALT(SGPT) $\leq 3 \times$ institutional ULN
(AST and/or ALT $\leq 5 \times \text{ULN}$ for patients with liver involvement)
- alkaline phosphatase $\leq 2.5 \times \text{ULN}$
($\leq 5 \times \text{ULN}$ for patients with documented liver involvement or bone metastases)
- creatinine
For adult patients (≥ 18 years of age):
 $\geq 30 \text{ mL/min/1.73 m}^2$ by Cockcroft-Gault

$\frac{(140 - \text{age}) \times (\text{weight in kg})}{72 \times (\text{serum creatinine in mg/dL})} \quad (\times 0.85 \text{ if female})$
--

For pediatric patients (< 18 years of age), a serum creatinine based on age and gender as follows:

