3.2 Exclusion Criteria

- 3.2.1 Any prior therapy must have been completed ≥ 4 weeks or, if known, ≥ 5 half-lives of the prior agent (whichever is shorter) prior to enrollment on protocol (minimum of 1 week between prior therapy and study enrollment), and the participant must have recovered to eligibility levels from prior toxicity. Patients should be at least 6 weeks out from nitrosoureas and mitomycin C. Prior definitive radiation should have been completed ≥ 4 weeks or palliative radiation should have been completed ≥ 2 weeks prior to study enrollment and all associated toxicities resolved to eligibility levels (patients on study may be eligible for palliative radiotherapy to non-targeted lesions after 2 cycles of therapy at the PI's discretion). Patients who have had prior monoclonal antibody therapy must have completed that therapy ≥ 6 weeks (or 3 half-lives of the antibody, whichever is shorter) prior to enrollment on protocol (minimum of 1 week between prior therapy and study enrollment). A patient who has received a cumulative dose of >350 mg/m² of anthracycline (regardless of cardioprotectant) may only be enrolled if their

ejection fraction measured by an echocardiogram is within normal institutional limits.

- 3.2.2 Prior treatment with anti-PD-1, or anti-PD-L1 therapeutic antibody or pathway-targeting agents.
- Patients who have received prior treatment with anti-CTLA-4 may be enrolled, provided the following requirements are met:
 - Minimum of 12 weeks from the first dose of anti-CTLA-4 and >6 weeks from the last dose
 - No history of severe immune-related adverse effects from anti-CTLA-4 (NCI CTCAE Grade 3 and 4)
- 3.2.3 Treatment with any other investigational agent within 4 weeks (or within five half-lives of the investigational product, whichever is shorter) prior to Cycle 1, Day 1 (minimum of 1 week between prior therapy and study enrollment). Patients must be ≥ 2 weeks since any investigational agent administered as part of a Phase 0 study (also referred to as an “early Phase I study” or “pre-Phase I study” where a sub-therapeutic dose of drug is administered) at the Coordinating Center PI’s discretion, and should have recovered to eligibility levels from any toxicities.
- 3.2.4 Treatment with systemic immunostimulatory agents (including, but not limited to, interferon- α or interleukin-2 [aldesleukin]) within 6 weeks prior to Cycle 1, Day 1.

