- 3.3.3 Imaging Studies - every participant should have an evaluation of known sites of disease, conducted via a CT scan of the chest/abdomen/pelvis. This scan may be done at the enrolling institution; alternatively, images or reports from scans conducted at an outside institution may be used. Either way, the scan, image, or report used to determine eligibility must be *at least* as recent as the time of disease progression determination on the patient's last treatment. Scans for baseline tumor measurements must be done within 28 days prior to the start of protocol therapy; radiographs used to determine eligibility can be used for baseline measurements if the scans were conducted ≤ 28 days prior to start of protocol therapy and the site investigator determines that they are of acceptable quality. At the discretion of the PI and as clinically indicated, the following imaging studies may also be performed: MRI or CT scan with contrast of the brain, MRI liver, or MRI for other disease sites.
- 3.3.4 Laboratory Evaluation - laboratory data are to be obtained within 8 days prior to both enrollment and start of protocol therapy:
- Hematological Profile: CBC with differential, hemoglobin, platelets
 - Biochemical Profile: ACTH, albumin, alkaline phosphatase (ALP), AM cortisol, bicarbonate, total bilirubin, BUN, calcium, chloride, creatinine, glucose, LDH, phosphorus, potassium, total protein, SGOT [AST], SGPT [ALT], sodium, TSH, free T4, amylase, lipase
 - Urinalysis
 - Serum or urine pregnancy test for female participants of childbearing potential
 - PT and PTT only for patients undergoing research biopsies
- 3.3.5 Cardiac Evaluation
- EKG - to be performed within 8 days prior to both enrollment and start of protocol therapy
 - ECHO - to be performed within 28 days prior to both enrollment and start of protocol therapy

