Patient enrollment for this study will be facilitated using the Slot Reservation System in conjunction with the registration system in OPEN. Prior to discussing protocol entry with the patient, all site staff must use the IWRS Slot Reservation System to ensure that a slot on the protocol is available to the patient. Once a slot reservation confirmation is obtained, site staff may then proceed to enroll the patient to this study. Slots can be reserved for a maximum of 14 calendar days.

The OPEN system will provide the site with a printable confirmation of registration and treatment information. Please print this confirmation for your records.

Following registration, patients should begin protocol treatment within 8 days. Issues that would cause treatment delays should be discussed with the Principal Investigator.

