5.2 General Concomitant Medication and Supportive Care Guidelines

Because there is a potential for interaction of atezolizumab with other concomitantly administered drugs, the case report form must capture the concurrent use of all other drugs, over-the-counter medications, or alternative therapies. The Principal Investigator should be alerted if the patient is taking any agent known to affect or with the potential for drug interactions. The study team should check a frequently-updated medical reference for a list of drugs to avoid or minimize use of. [Appendix B](#) (Patient Drug Information Handout and Wallet Card) is available.

Palliative radiotherapy to non-targeted lesions may be permitted for patients receiving atezolizumab after completing 2 cycles of therapy and achieving stable or responding disease, at the Principal Investigator's discretion.

Drugs to be avoided:

- Traditional herbal or homeopathic or natural medicines should be limited and used at the discretion of the investigator
- Ingredients for such medicines have not been fully studied, and their use may result in unanticipated drug-drug interactions that may cause or confound assessment of toxicity.
- Immunostimulatory agents, including but not limited to interferon (IFN)- α , IFN- γ , anti-TNF- α , or IL-2 (aldesleukin) (prohibited prior to and during the study and for 10 weeks after the last dose of atezolizumab; see Section [3.2.4](#)). These agents, in combination with atezolizumab, could potentially increase the risk for autoimmune conditions.
- Immunosuppressive medications, including but not limited to cyclophosphamide, azathioprine, methotrexate, and thalidomide. These agents could potentially alter the activity and the safety of atezolizumab.
- Live vaccines and live, attenuated vaccines (prohibited during the study and for 100 days after the last dose of study drug).
- Initiation of granulocyte colony-stimulating factors (e.g., filgrastim and biosimilar products, sargramostim, and/or pegfilgrastim) should be discussed with the Medical Monitor.

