11.2.2 Disease Parameters

Measurable Disease. Measurable lesions are defined as those that can be accurately measured in at least one dimension (longest diameter to be recorded) as ≥ 20 mm (≥ 2 cm) by chest x-ray or as ≥ 10 mm (≥ 1 cm) with CT scan, MRI, or calipers by clinical exam. All tumor measurements must be recorded in millimeters (or decimal fractions of centimeters).

Malignant Lymph Nodes. To be considered pathologically enlarged and measurable, a lymph node must be ≥ 15 mm (≥ 1.5 cm) in short axis when assessed by CT scan (CT scan slice thickness recommended to be no greater than 5 mm [0.5 cm]). At baseline and in follow-up, only the short axis will be measured and followed.

Non-Measurable Disease. All other lesions (or sites of disease), including small lesions (longest diameter < 10 mm [< 1 cm] or pathological lymph nodes with ≥ 10 to < 15 mm [≥ 1 to < 1.5 cm] short axis), are considered non-measurable disease. Bone lesions, leptomeningeal disease, ascites, pleural/pericardial effusions, lymphangitis cutis/pulmonitis, inflammatory breast disease, and abdominal masses (not followed by CT or MRI), are considered as non-measurable.

Note: Cystic lesions that meet the criteria for radiographically defined simple cysts should not be considered as malignant lesions (neither measurable nor non-measurable) since they are, by definition, simple cysts.

‘Cystic lesions’ thought to represent cystic metastases can be considered as measurable lesions, if they meet the definition of measurability described above. However, if non-cystic lesions are

present in the same patient, these are preferred for selection as target lesions.

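### As written, a soft-tissue, nodal or lung lesion irradiated shortly before entry can be a target lesion with a pre-radiotherapy baseline, so its shrinkage can count in the primary ORR

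*Combined protocol and SAP*

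**What the plan says.** **Radiotherapy before entry.** Section 3.2.1 requires that "palliative radiation should have been completed ≥ 2 weeks prior to study enrollment and all associated toxicities resolved to eligibility levels". Definitive radiation must have ended at least 4 weeks before enrollment. Neither condition refers to the lesion treated.

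**Radiotherapy on study.** Section 5.2 states: "Palliative radiotherapy to non-targeted lesions may be permitted for patients receiving atezolizumab after completing 2 cycles of therapy and achieving stable or responding disease". Section 3.2.1 has a shorter version: "patients on study may be eligible for palliative radiotherapy to non-targeted lesions after 2 cycles of therapy at the PI's discretion". Both keep on-study radiotherapy away from target lesions.

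**Baseline scan.** Section 3.3.3: "Scans for baseline tumor measurements must be done within 28 days prior to the start of protocol therapy". The scan used for eligibility must be at least "as recent as the time of disease progression determination on the patient's last treatment". Section 11.2.3 asks for baseline evaluation near the start of treatment, with 4 weeks as the outer limit. Section 4.3.1 adds: "Following registration, patients should begin protocol treatment within 8 days".

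**Lesion rules.** Eligibility (3.1.2) needs "at least one lesion that can be accurately measured in at least one dimension". Section 11.2.2 says: "Measurable lesions are defined as those that can be accurately measured in at least one dimension", with size thresholds, and classes bone lesions as non-measurable. Targets are chosen by size, organ representation and reproducibility, up to 2 per organ and 5 in total. Earlier irradiation is not mentioned.

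**Scoring.** PR is a fall of at least 30% from the baseline sum (11.2.4.1). Section 13.1 puts all eligible treated adults in the primary and interim response analyses. It stops a cohort at 0 responses in 9 and calls it positive at 3 or more in 17.

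**The concern.** The plan accepts that radiotherapy should not touch a lesion from which drug effect is read, but applies this only after treatment starts. Before entry, nothing in the text stops the irradiated lesion from being the measured one, and nothing requires the baseline scan to follow the radiotherapy. By contrast, Section 3.1.8 does require imaging after local treatment of brain metastases.

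The situation is plausible. Section 3.1.3 admits newly diagnosed metastatic patients on clinical progression and gives rising tumor pain as the example; pain is a usual reason for palliative radiotherapy. Section 2.4 supports the CCS cohort partly with a complete response to pembrolizumab given with radiotherapy, where the two effects cannot be separated.

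The decisions turn on very few responses: one keeps a cohort open and three make it positive. A single response caused by radiotherapy could therefore change a decision.

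**Working it through.** **1. Timing.** Count days from the start of treatment (day 0). Let g be the gap from enrollment to start, 0 to 8 days (4.3.1). Palliative radiotherapy must end by day -(14 + g) (3.2.1). With the scan at day -28 (3.3.3), it may end up to 28 - 14 - g days after the scan:

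- g = 0: 14 days
- g = 8: 6 days

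Definitive radiotherapy must end by day -(28 + g), so a scan within 28 days cannot precede its completion. An irradiated lesion can still be a target in that case, but its baseline is then measured after the radiotherapy.

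**2. Shrinkage needed.** If the irradiated lesion makes up a share w of the baseline sum and other targets do not change, PR needs that lesion to shrink by 0.30/w:

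- w = 1: 30%
- w = 1/2: 60%
- w = 1/3: 90%
- w below 0.30: not possible from that lesion alone

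One measurable lesion is enough for eligibility, so w = 1 can occur.

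**3. The plan's own figures.** With X1 responses in the first 9 patients and X2 in the next 8, at response rate p:

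P(negative) = P(X1=0) + P(X1=1)·P(X2≤1) + P(X1=2)·P(X2=0)

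At p = 0.05: 0.6302 + 0.2985 × 0.9428 + 0.0629 × 0.6634 = 0.9534. The false-positive probability is 0.0466 and early stopping 0.630. At p = 0.25 power is 0.812. Section 13.1 states .95, .63 and 81%, so all three reproduce.

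**4. Effect of radiotherapy-only responses.** Let r be the chance that a patient who would not respond to the drug is scored a confirmed PR because of radiotherapy. The effective rate is 0.05 + 0.95r. The documents give no value for r; these are assumptions.

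| r (assumed) | Effective rate | Early stop | False positive |
|---|---|---|---|
| 0 | 0.0500 | 0.630 | 0.047 |
| 0.1% | 0.0510 | 0.625 | 0.049 |
| 0.5% | 0.0548 | 0.602 | 0.058 |
| 1% | 0.0595 | 0.576 | 0.071 |
| 2% | 0.0690 | 0.526 | 0.101 |

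Here r is the share of patients with an irradiated target times the share of those reaching a confirmed PR from radiotherapy: 2% × 5% gives 0.1%, and 10% × 20% gives 2%.

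**5. One such response in the first nine.** Early stopping becomes impossible. The cohort is positive if at least 2 of the other 16 respond: 1 - 0.95^16 - 16 × 0.05 × 0.95^15 = 1 - 0.4401 - 0.3706 = 0.189.

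**The case against.** - **RECIST 1.1 is the adopted standard (11.1).** The cited guideline may cover irradiated lesions. It is not among the documents, so this cannot be checked. What can be shown is that 11.2.2 writes out the lesion rules without one. A reader might infer that the trial has no rule at all; the documents do not support going that far.
- **Bone lesions cannot be targets, and chondrosarcoma resists radiation.** Both stand. Section 2.2 calls conventional chondrosarcoma typically refractory, and 2.4 describes chondrosarcoma generally as radio-resistant. This leaves mainly CCS, which 2.1 describes as a soft-tissue tumor with mostly pulmonary distant metastases.
- **The scan-then-irradiate sequence is narrow.** It needs an early scan and a short course with toxicity resolved, despite 11.2.3. If radiotherapy was the last treatment, 3.3.3 arguably already calls for a later scan. This lowers the frequency. However, the 3.3.3 rule concerns the eligibility scan and the patient's progression, not the irradiated lesion.
- **Response must last.** First restaging is after Cycle 3 (3 × 3 = 9 weeks) and confirmation at least 4 weeks later, so about 13 weeks without new lesions or non-target progression. With an inactive drug this argues against high values of r. It does not separate lasting radiotherapy shrinkage from drug effect.
- **Independent review (11.2.7).** Reading files alongside images could reveal recent radiotherapy, but the review is only recommended.

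**Conclusion.** The gap is real. The washout, scan-window and target-selection rules, followed exactly, can credit radiotherapy shrinkage to atezolizumab in the primary ORR. It applies to soft-tissue, nodal and lung lesions, and mainly to CCS.

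Its size is unknown. The shift from 0.047 is negligible at r = 0.1% (0.049) and material at r = 2% (0.101), and nothing in the documents locates r in that range. The 0.189 is conditional on one radiotherapy-driven response among the first nine patients. A reader might infer that the stated .95 probability of a negative result is wrong or that inflation is to be expected. Neither follows: the .95 reproduces, and it fails only if r exceeds about 0.15%, a low threshold chiefly because the design has little slack (0.0466 against 0.05).

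A reader might also see a second defect in the on-study rules, because 3.2.1 omits the condition in 5.2 that disease be stable or responding. That mismatch is minor: both sections confine on-study radiotherapy to non-target lesions. A sensitivity count built on on-study radiotherapy would not address the pre-entry gap.

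**What to change.** 1. **11.2.2:** a previously irradiated lesion may be a target only if progression in that lesion is documented after the radiotherapy; otherwise it is non-target.
2. **3.3.3 and Section 5:** the baseline tumor scan must follow completion of any pre-study radiotherapy and fall within 28 days before treatment.
3. **CRF:** record the date and field of pre-study radiotherapy.

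The sample size and decision rules do not change.

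**Cost.** A patient whose only measurable lesion was irradiated and has not since progressed becomes ineligible. An occasional genuine drug response in such a lesion will not be counted. Some scans must be timed later or repeated. The rule also reaches radiotherapy given long before entry, unless progression in that lesion is on record.

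The accrual loss is small under an assumed range. If a share e of candidates is lost, filling 3 × 17 = 51 adult places needs 51/(1 - e) - 51 extra candidates: 0.5 at e = 1% and 2.7 at e = 5%. At 1.5 patients per month, the middle of the 1 to 2 in Section 13.2, that is about 0.3 to 1.8 months.

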3.3 Screening Evaluation

Patient eligibility screening tests will be performed as described below. Eligibility history, physical examination, laboratory evaluations, urinalysis, and EKG are to be conducted within 8 days prior to enrollment. As noted in Section [5](#), if protocol therapy is started within 8 days of these eligibility screening evaluations, values from the screening evaluations may be used as baseline measurements; if >8 days have passed since the screening evaluations, the medical history, physical examination, laboratory evaluations, urinalysis, and EKG must be repeated prior to starting protocol therapy. ECHO must be done within 28 days prior to enrollment. ECHO and baseline imaging scans must be done within 28 days prior to the start of protocol therapy; eligibility screening results (ECHO and radiographs) can be used if done ≤28 days prior to start of protocol therapy and the site investigator determines that they are of acceptable quality.

- 3.3.1 Histologic confirmation: For patients enrolling on the basis of CCS diagnosis, in the absence of documented *EWSR1* translocation, histological confirmation of CCS will be required at the enrollment site prior to enrollment. Reports from outside institutions will

be accepted for documentation of *EWSR1/ATF1* or *EWSR1/CREB1* translocation, grade 2 or 3 conventional chondrosarcoma, or dedifferentiated chondrosarcoma.

- 3.3.2 History and Physical Examination - complete history and physical examination (including height, weight, vital signs, and performance score [ECOG, Karnofsky, or Lansky, see Appendix A]) will be conducted within 8 days prior to both enrollment and the start of protocol therapy.
- 3.3.3 Imaging Studies - every participant should have an evaluation of known sites of disease, conducted via a CT scan of the chest/abdomen/pelvis. This scan may be done at the enrolling institution; alternatively, images or reports from scans conducted at an outside institution may be used. Either way, the scan, image, or report used to determine eligibility must be *at least* as recent as the time of disease progression determination on the patient's last treatment. Scans for baseline tumor measurements must be done within 28 days prior to the start of protocol therapy; radiographs used to determine eligibility can be used for baseline measurements if the scans were conducted ≤ 28 days prior to start of protocol therapy and the site investigator determines that they are of acceptable quality. At the discretion of the PI and as clinically indicated, the following imaging studies may also be performed: MRI or CT scan with contrast of the brain, MRI liver, or MRI for other disease sites.
- 3.3.4 Laboratory Evaluation - laboratory data are to be obtained within 8 days prior to both enrollment and start of protocol therapy:
- Hematological Profile: CBC with differential, hemoglobin, platelets
 - Biochemical Profile: ACTH, albumin, alkaline phosphatase (ALP), AM cortisol, bicarbonate, total bilirubin, BUN, calcium, chloride, creatinine, glucose, LDH, phosphorus, potassium, total protein, SGOT [AST], SGPT [ALT], sodium, TSH, free T4, amylase, lipase
 - Urinalysis
 - Serum or urine pregnancy test for female participants of childbearing potential
 - PT and PTT only for patients undergoing research biopsies
- 3.3.5 Cardiac Evaluation
- EKG - to be performed within 8 days prior to both enrollment and start of protocol therapy
 - ECHO - to be performed within 28 days prior to both enrollment and start of protocol therapy

